APPENDIX 4 MANAGEMENT ALGORITHMS

These general guidelines constitute guidance to the Investigator and may be supplemented by discussions with the Medical Monitor representing the Sponsor. The guidance applies to all immuno-oncology agents and regimens.

A general principle is that differential diagnoses should be diligently evaluated according to standard medical practice. Non-inflammatory etiologies should be considered and appropriately treated.

[figure not shown]
Corticosteroids are a primary therapy for immuno-oncology drug-related adverse events. The oral equivalent of the recommended IV doses may be considered for ambulatory patients with low-grade toxicity. The lower bioavailability of oral corticosteroids should be taken into account when switching to the equivalent dose of oral corticosteroids.

Consultation with a medical or surgical specialist, especially prior to an invasive diagnostic or therapeutic procedure, is recommended.

The frequency and severity of the related adverse events covered by these algorithms will depend on the immuno-oncology agent or regimen being used.

GI Adverse Event Management Algorithm

Rule out non-inflammatory causes. If non-inflammatory cause is identified, treat accordingly and continue I-O therapy. Opiates/narcotics may mask symptoms of perforation. Infliximab should not be used in cases of perforation or sepsis.

[figure not shown]

Patients on IV steroids may be switched to an equivalent dose of oral corticosteroids (e.g. prednisone) at start of tapering or earlier, once sustained clinical improvement is observed. Lower bioavailability of oral corticosteroids should be taken into account when switching to the equivalent dose of oral corticosteroids.

25-Jun-2019

Renal Adverse Event Management Algorithm

Rule out non-inflammatory causes. If non-inflammatory cause, treat accordingly and continue I-O therapy.

[figure not shown]

Patients on IV steroids may be switched to an equivalent dose of oral corticosteroids (e.g. prednisone) at start of tapering or earlier, once sustained clinical improvement is observed. Lower bioavailability of oral corticosteroids should be taken into account when switching to the equivalent dose of oral corticosteroids.

25-Jun-2019

Pulmonary Adverse Event Management Algorithm

Rule out non-inflammatory causes. If non-inflammatory cause, treat accordingly and continue I-O therapy. Evaluate with imaging and pulmonary consultation.

[figure not shown]

Patients on IV steroids may be switched to an equivalent dose of oral corticosteroids (e.g. prednisone) at start of tapering or earlier, once sustained clinical improvement is observed. Lower bioavailability of oral corticosteroids should be taken into account when switching to the equivalent dose of oral corticosteroids

25-Jun-2019

Hepatic Adverse Event Management Algorithm

Rule out non-inflammatory causes. If non-inflammatory cause, treat accordingly and continue I-O therapy. Consider imaging for obstruction.

[figure not shown]
Patients on IV steroids may be switched to an equivalent dose of oral corticosteroids (e.g. prednisone) at start of tapering or earlier, once sustained clinical improvement is observed. Lower bioavailability of oral corticosteroids should be taken into account when switching to the equivalent dose of oral corticosteroids.

*The recommended starting dose for grade 4 hepatitis is 2 mg/kg/day methylprednisolone IV.

25-Jun-2019

Endocrinopathy Adverse Event Management Algorithm

Rule out non-inflammatory causes. If non-inflammatory cause, treat accordingly and continue I-O therapy. Consider visual field testing, endocrinology consultation, and imaging.

[figure not shown]

Patients on IV steroids may be switched to an equivalent dose of oral corticosteroids (e.g. prednisone) at start of tapering or earlier, once sustained clinical improvement is observed. Lower bioavailability of oral corticosteroids should be taken into account when switching to the equivalent dose of oral corticosteroids.

25-Jun-2019

Skin Adverse Event Management Algorithm

Rule out non-inflammatory causes. If non-inflammatory cause, treat accordingly and continue I-O therapy.

Patients on IV steroids may be switched to an equivalent dose of oral corticosteroids (e.g. prednisone) at start of tapering or earlier, once sustained clinical improvement is observed. Lower bioavailability of oral corticosteroids should be taken into account when switching to the equivalent dose of oral corticosteroids.

[figure not shown]
*Refer to NCI CTCAE v4 for term-specific grading criteria.

^If SJS/TEN is suspected, withhold I-O therapy and refer patient for specialized care for assessment and treatment. If SJS or TEN is diagnosed, permanently discontinue I-O therapy.

25-Jun-2019

Neurological Adverse Event Management Algorithm

[figure not shown]
Rule out non-inflammatory causes. If non-inflammatory cause, treat accordingly and continue I-O therapy.

Patients on IV steroids may be switched to an equivalent dose of oral corticosteroids (e.g. prednisone) at start of tapering or earlier, once sustained clinical improvement is observed. Lower bioavailability of oral corticosteroids should be taken into account when switching to the equivalent dose of oral corticosteroids.

25-Jun-2019

Myocarditis Adverse Event Management Algorithm

Patients on IV steroids may be switched to an equivalent dose of oral corticosteroids (eg, prednisone) at start of tapering or earlier, once sustained clinical improvement is observed. Lower bioavailability of oral corticosteroids should be taken into account when switching to the equivalent dose of oral corticosteroids.

Prophylactic antibiotics should be considered in the setting of ongoing immunosuppression.

ATG = anti-thymocyte globulin; BNP = B-type natriuretic peptide; ECG = electrocardiogram; IV = intravenous; MRI = magnetic resonance imaging

25-Jun-2019

APPENDIX 5 ECOG, KARNOFSKY, AND LANSKY PERFORMANCE STATUS

PERFORMANCE STATUS CRITERIA: ECOG Score	
ECOG (Zubrod)	
Score	Description
0	Fully active; able to carry on all pre-disease performance without restriction
1	Restricted in physically strenuous activity but ambulatory and able to carry out work of a light or sedentary nature, e.g., light house work, office work.
2	Ambulatory and capable of all self care but unable to carry out any work activities; up and about more than 50% of waking hours.
3	Capable of only limited self care; confined to bed or chair more than 50% of waking hours.
4	Completely disabled; cannot carry on any self care; totally confined to bed or chair.

PERFORMANCE STATUS CRITERIA: Karnofsky and Lansky		
Score	Karnofsky Description	Lansky Description
100	Normal; no complaints; no evidence of disease	Fully active, normal
90	Able to carry on normal activity; minor signs or symptoms of disease.	Minor restrictions in physically strenuous activity
80	Normal activity with effort; some signs or symptoms of disease.	Active, but tires more quickly
70	Cares for self; unable to carry on normal activity or to do active work.	Substantial restriction of, and less time spent, in play activity
60	Requires occasional assistance, but is able to care for most of their personal needs.	Out of bed, but minimal active play; keeps busy with quiet activities
50	Requires considerable assistance and frequent medical care.	Gets dressed, but inactive much of day; no active play, able to participate in quiet play
40	Disabled; requires special care and assistance.	Mostly in bed; participates in some quiet activities
30	Severely disabled; hospital admission is indicated although death not imminent.	In bed; needs assistance even for quiet play
20	Very sick; hospital admission necessary; active supportive treatment necessary.	Often sleeping; play limited to passive activities
10	Moribund; fatal processes progressing rapidly.	No play; does not get out of bed
0	Dead	Unresponsive

APPENDIX 6 RESPONSE CRITERIA MODIFIED FROM IMWG FOR MULTIPLE MYELOMA

Response Subcategory	Response Criteria ¹
Stringent Complete Response (sCR)	CR, as defined below, plus the following: Normal FLC ratio and absence of clonal cells in bone marrow ² by immunohistochemistry or immunofluorescence. ³
Complete Response (CR)	
 Negative immunofixation on the serum and urine. ≤ 5% plasma cells in bone marrow.
Very Good Partial Response (VGPR)	Serum and urine M-protein detectable by immunofixation but not on electrophoresis or ≥ 90% reduction in serum M-protein level plus urine M-protein level < 100 mg per 24 hour.
Partial Response (PR)	≥ 50% reduction of serum M-protein and reduction in 24-hour urinary M-protein by ≥90% or to < 200 mg per 24 hour.
Minor (Minimal) Response (MR)	Subjects who have reduction in M-protein but do not meet the criteria for PR are classified as MR if they meet all the following definition: 
 Between 25 - 49% reduction in serum M-protein. Between 50 - 89% reduction in urinary light chain excretion which still exceeds 200 mg/24 hours. If a skeletal survey is performed, no development of lytic lesions.
Stable Disease (SD)	Not meeting criteria for CR, VGPR, PR, MR, or progression.
Progression Subcategory	Progression Criteria
Progressive disease ⁴	Requires an increase of ≥ 25% from lowest response level (nadir) in any one or more of the following: 
 Serum M-component (the absolute increase must be ≥ 0.5 g/dL).⁵ Urine M-component (the absolute increase must be ≥ 200 mg/24 hour). Bone marrow plasma cell percentage: the absolute % must be ≥ 10%. Definite development of new bone lesions or soft tissue plasmacytomas. Development of hypercalcemia (corrected serum calcium > 11.5 mg/dL or 2.65 mmol/L) that can be attributed solely to the plasma cell proliferative disorder.
Progression to Active Myeloma	Evidence of progression based on IMWG criteria for progressive disease in myeloma and any one or more of the following felt related to the underlying clonal plasma cell proliferative disorder: 
 Development of new soft tissue plasmacytomas or bone lesions. Hypercalcemia (> 11 mg/dL) Decrease in hemoglobin of ≥ 2 g/dL Rise in serum creatinine by 2 mg/dL or more

1 All response categories require 2 consecutive assessments made at any time before the institution of any new therapy; all categories also require no known evidence of progressive or new bone lesions if radiographic studies

- were performed. Radiographic studies are not required to satisfy these response requirements. The second of the 2 consecutive assessments should occur at the next planned tumor assessment.
- 2 Confirmation with repeat bone marrow biopsy not needed.
 - 3 Presence or absence of clonal cells is based upon the κ/λ . An abnormal κ/λ ratio by immunohistochemistry and/or immunofluorescence requires a minimum of 100 plasma cells for analysis. An abnormal ratio reflecting presence of an abnormal clone is κ/λ of $> 4:1$ or $< 1:2$.
 - 4 To be used for calculation of time to progression and progression-free survival endpoints for all subjects, including those in CR (includes primary progressive disease and disease progression on or off therapy).
 - 5 For progressive disease, serum M-component increase of ≥ 1 gm/dl is sufficient to define progression if starting M-component is ≥ 5 g/dL.

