The **Treatment Period** consists of up to twelve 8-week treatment cycles. Each treatment cycle comprises 4 doses of relatlimab administered on Days [REDACTED]. Subjects will be allowed to continue study therapy until the first occurrence of either: (1) meeting criteria for discontinuation as described in [Section 4.3.5](#), (2) completion of the maximum number of twelve [REDACTED] cycles, (3) confirmed progressive disease (PD), or (4) clinical deterioration. Subjects who discontinue treatment will enter a 135-day **Clinical Follow-Up Period**. After completion of the **Clinical Follow-Up period**, HL patients in Parts C and D will enter the **Survival Follow-Up period**. For participants who discontinue study treatment prior to disease progression, diagnostic imaging will be obtained every 6 months after the first clinical follow-up in year 1 and in year 2, and annually thereafter for a total of 5 years maximum (since the first dose of the study drug) until disease progression. **Re-Challenge** may be conducted in selected cases at progression.

If subjects progress during the clinical follow-up period or the survival follow-up period, they could further receive therapy with relatlimab alone or in combination with nivolumab (Re-Challenge period) as long as the risk:benefit ratio is considered favorable by the Investigator and the Medical Monitor and eligibility criteria is met ([Section 3.3](#)). The original dose and schedule and protocol rules would apply accordingly. Thus, subjects could receive therapy for up to [REDACTED] additional eight-week cycles. Subjects will not be re-challenged a second time. Collection of archival tissue (baseline) and tumor biopsies (baseline and on-treatment) will be optional for subjects enrolled for re-challenge. PK and biomarker monitoring will be limited ([Sections 5.5](#) and [5.7](#)).

A study schematic is shown in Figure 3.1-2.

Figure 3.1-2: Study Schematic for Parts A,¹ B, C, and D

- 1 Part A DLT period: 8 weeks
- 2 Treatment beyond progression may be considered in selected subjects as described in Protocol [Section 4.3.4](#)
- 3 WOCBP will have additional follow-up assessments through Day 165 for home pregnancy tests

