 - v) Subjects enrolled in Part A and B must consent to allow a pre-treatment unilateral bone marrow biopsy and/or aspirate to be performed (all subjects). Subjects who had a bone marrow biopsy and/or aspirate since completion of their last therapy may not use those results in lieu of the required baseline bone marrow biopsy.
 - vi) Subjects enrolled in the [REDACTED] mg monotherapy escalation cohort must consent to allow on-treatment unilateral bone marrow biopsy and/or aspirate to be performed at Week 4 during cycle 1 independently of the disease status. Subjects unable to provide a fresh on-treatment tumor biopsy are not eligible.
 - vii) Subjects enrolled in the [REDACTED] mg monotherapy escalation cohort must consent to allow on treatment unilateral bone marrow biopsy and/or aspirate to be performed to document complete response (CR), partial response (PR), or progressive disease (PD) shall be performed as clinically indicated.
 - viii) Subjects enrolled in Part B, expansion monotherapy cohort, must consent to allow on-treatment unilateral bone marrow biopsy and/or aspirate to be performed (first three subjects in each cohort) at Week 4 during cycle 1 independently of the disease status. Subjects unable to provide a fresh on-treatment tumor biopsy are not eligible.
 - ix) Subjects enrolled in Part B, expansion monotherapy, must consent to allow on treatment unilateral bone marrow biopsy and/or aspirate to be performed to document

complete response (CR), partial response (PR), or progressive disease (PD) shall be performed as clinically indicated.

- c) Consent for biopsy samples in subjects with Multiple Myeloma.
 - i) Subjects must consent to allow a pre-treatment unilateral bone marrow biopsy and/or aspirate to be performed (all subjects).

2) Target Population

- a) Subjects must have histologic or cytologic confirmation of chronic lymphocytic leukemia, Hodgkin lymphoma, Non-Hodgkin lymphoma, or Multiple Myeloma and have relapsed following prior treatment or been refractory to prior treatment.
- b) Part A Dose Escalation Relatlimab Monotherapy.
 - i) Chronic lymphocytic leukemia.
 - ii) Hodgkin lymphoma.
 - iii) Non-Hodgkin lymphoma.
 - iv) Multiple Myeloma by modified IMWG Criteria⁶³ (Appendix 6).
- c) Part B Cohort Expansion Relatlimab Monotherapy [REDACTED] mg.
 - i) Chronic lymphocytic leukemia.
 - ii) Diffuse large B-cell lymphoma.
 - iii) Indolent non-Hodgkin lymphoma.
 - iv) Hodgkin Lymphoma.

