5.3 Safety Assessments

Adverse events will be assessed continuously during the study and for 135 days after the last treatment. Adverse events will be evaluated according to NCI CTCAE version 4.0 and should be followed per requirements in [Sections 6.1.1](#) and [6.2.1](#). Adverse events will be coded using the most current version of Medical Dictionary for Regulatory Activities (MedDRA) and reviewed for potential significance and importance.

Protocol-specified assessments are described in [Table 5.1-1](#) (Screening Procedural Outline), [Table 5.1-2](#) (On-Treatment Procedural Outline), and [Table 5.1-3](#) (Follow-Up Procedural Outline).

5.3.1 *Imaging Assessment for the Study*

Any incidental findings of potential clinical relevance that are not directly associated with the objectives of the protocol should be evaluated and handled by the Study Investigator as per standard medical/clinical judgment.

5.3.2 *Genomic Analysis*

In order to identify potential polymorphisms associated with safety and efficacy of relatlimab, selected genes will be evaluated for single nucleotide polymorphisms (SNP). Analysis will include but not be limited to sequence polymorphisms linked to genes and pathways associated with [REDACTED] and [REDACTED]

██████████ DNA may also be utilized for DNA sequencing to identify germline sequences to compare with tumor sequences.

5.3.3 **Laboratory Test Assessments**

A central/local laboratory will perform the analyses and will provide reference ranges for these tests.

Clinical laboratories will be assessed at the time points indicated in [Table 5.1-1](#) (Screening Procedural Outline), [Table 5.1-2](#) (On-Treatment Procedural Outline), and [Table 5.1-3](#) (Follow-Up Procedural Outline).

At screening, sites should collect samples during the timeframes indicated in Table 5.1-1 and ensure that results required for eligibility are verified prior to registration. During treatment, unless otherwise indicated in Table 5.1-2, results of clinical laboratory test must be reviewed prior to dosing.

The following clinical laboratory tests will be performed:

Hematology (Local Laboratory)

Complete blood count (CBC) with differential
Platelet count
INR (screening only)

Serum Chemistry (Local Laboratory)

Aspartate aminotransferase (AST)	C-reactive protein
Alanine aminotransferase (ALT)	Albumin
Total bilirubin	Sodium
Alkaline phosphatase	Potassium
Lactate dehydrogenase (LDH)	Chloride
Creatinine	CO ₂
Blood urea nitrogen (BUN)	Calcium

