Results of all laboratory tests required by this protocol must be provided to BMS, either recorded on the laboratory pages of the CRF or by another mechanism as agreed upon between the investigator and BMS (eg, provided electronically). If the units of a test result differ from those printed on the CRF, the recorded laboratory values must specify the correct units. Any abnormal

laboratory test result considered clinically significant by the investigator must be recorded on the appropriate AE page of the CRF (see [Section 6.3](#)).

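### The hypercalcemia limit for myeloma progression in Appendix 6 is given in two units that do not convert: 11.5 mg/dL is 2.87 mmol/L, not 2.65 mmol/L.

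*Combined protocol and SAP*

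**What the plan says.** The progressive disease row of Appendix 6 lists several findings, any one of which can establish progression in a myeloma subject. One of them is "Development of hypercalcemia (corrected serum calcium > 11.5 mg/dL or 2.65 mmol/L". The hypercalcemia must be attributable to the plasma cell disorder alone. The row opens with a general requirement of a rise of at least 25% from the lowest response level, which on a literal reading covers this item too.

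Footnote 4, attached to this row, says what the category is for: "To be used for calculation of time to progression and progression-free survival endpoints for all subjects, including those in CR".

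Other sections settle where the criterion applies and how calcium is obtained:

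- Section 3.3.1 lists "Multiple Myeloma by modified IMWG Criteria" as a target disease in Part A. Parts B, C and D list other diseases.
- Section 5.3.3 places calcium in the panel headed "Serum Chemistry (Local Laboratory"). It also provides for differing units: "If the units of a test result differ from those printed on the CRF, the recorded laboratory values must specify the correct units".
- Section 3.1 ends study therapy at, among other events, "3) confirmed progressive disease (PD), or (4) clinical deterioration".

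No conversion rule is given, and nothing says which unit takes precedence.

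**The concern.** A limit written in two units is normally one limit. The CLL criteria in Appendix 2 use paired units that way, and those pairs convert exactly (20 g/L with 2 g/dL, 100 g/L with 10 g/dL). The calcium pair does not. An investigator who applies the figure in the laboratory's own unit would be using a different rule from one whose laboratory reports in the other unit.

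At stake is whether, and when, a myeloma subject is recorded as having progressed. That call bears on continuing study drug (Sections 3.1, 3.5 and 5.4) and on any summary of antitumor activity under monotherapy, which is an exploratory objective in Section 1.3.3.

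**Working it through.** **Inputs.** The limits 11.5 mg/dL and 2.65 mmol/L come from Appendix 6. The molar mass of calcium, 40.078 g/mol, is a physical constant that the documents do not give.

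**Formula.** mmol/L = (mg/dL × 10) / 40.078. In reverse, mg/dL = mmol/L × 40.078 / 10.

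**Trying to reproduce the plan's pair.**

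- 11.5 × 10 / 40.078 = 2.869, so 2.87 mmol/L. The plan prints 2.65.
- 2.65 × 40.078 / 10 = 10.62 mg/dL. The plan prints 11.5.

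**Could rounding or another unit explain it?**

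- Molar mass 40.0 (the rounded factor 0.25) gives 2.875 mmol/L and 10.60 mg/dL.
- Factor 0.2495 gives 2.869 mmol/L and 10.62 mg/dL.
- In mEq/L, 11.5 mg/dL is 2 × 2.869 = 5.74.
- For the pair to be equal, the molar mass would have to be 115 / 2.65 = 43.4 g/mol.

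None of these reconciles the figures.

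**Size of the gap.** 11.5 − 10.62 = 0.88 mg/dL, and 2.87 − 2.65 = 0.22 mmol/L. Relative to 2.65 that is 0.219 / 2.65 = 8.3%.

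**Values affected.** A corrected calcium above 10.62 and up to 11.5 mg/dL (above 2.65 and up to 2.87 mmol/L) exceeds one figure and not the other. For example, 11.0 mg/dL is 11.0 × 10 / 40.078 = 2.74 mmol/L, which is over 2.65 mmol/L but not over 11.5 mg/dL.

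**If the 25% rise also applies.**

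- A rise of exactly 25% ends at 11.5 mg/dL from a nadir of 11.5 / 1.25 = 9.2 mg/dL, and at 10.62 mg/dL from a nadir of 10.62 / 1.25 = 8.5 mg/dL.
- The two figures can therefore disagree only for nadirs up to 9.2 mg/dL, and over the whole gap only for nadirs up to about 8.5 mg/dL.
- The conflict narrows but remains. A rise from 8.6 to 11.0 mg/dL is 11.0 / 8.6 − 1 = 28%, and it meets the limit in mmol/L and not in mg/dL.

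**The case against.** The arithmetic cannot be answered, but the consequences can easily be overstated. Four stronger readings are tempting.

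*Sites do classify the same value differently.* A reader might infer this. The documents show only that it could happen: laboratories are local and units may differ. They do not show that any site treating myeloma subjects reports calcium in mmol/L. If *or* means that either figure suffices, every site should reach the same answer after conversion. In that case 2.65 mmol/L always governs and 11.5 mg/dL is redundant, which is still a drafting error but a different one.

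*Raised calcium alone settles progression.* It does not. Attribution solely to the plasma cell disorder is required, and perhaps the 25% rise as well. Nor does progression always end treatment: Section 3.1 refers to confirmed progression, and Section 4.3.4 allows treatment beyond initial progression under conditions.

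*The trial's efficacy results are exposed.* Footnote 4 mentions time to progression and PFS, but Section 8.3.2.3 introduces its efficacy endpoints for Part D, which enrolls Hodgkin lymphoma and DLBCL. PFS is exploratory there, and time to progression is not an endpoint in Section 8. The DOR definition cites Appendix 6, but Part D has no myeloma subjects.

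*There is a third conflicting limit.* The next row of Appendix 6 contains "Hypercalcemia (> 11 mg/dL"). That row, for progression to active myeloma, is a separate category with its own conditions, and footnote 4 is not attached to it. A different number there is not part of this conversion error.

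It is also fair to say that Part A escalation is described as finished, since the MTD was not reached and the Part B dose has been chosen. The remaining effect is then mostly on data already collected. These points limit the impact. They do not make the two figures agree.

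**Conclusion.** The error is real and small in reach. The stated limit is internally inconsistent by 0.88 mg/dL (about 8%) on either reading of *or*. It can change the classification only of Part A myeloma subjects with a corrected calcium above 10.62 and up to 11.5 mg/dL, attributed solely to the plasma cell disorder and, read literally, at least 25% above nadir. For them it touches the progression call, the decision on continuing treatment, and the exploratory monotherapy summaries. The primary safety endpoint and the Part D co-primary ORR and DOR are unaffected.

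The conversion rests only on the molar mass of calcium. Divergence between sites further assumes that units differ in practice and that each site applies the figure in its own unit. The documents give neither the number of myeloma subjects nor any calcium values, so the number of affected calls cannot be estimated. They also do not show which figure is intended.

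**What to change.** The sponsor should reconcile the two figures in Appendix 6, so that one intended threshold appears with its correct conversion into the other unit. Which threshold that is remains for the sponsor to determine.

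The sponsor should then list Part A myeloma assessments with a corrected calcium between 10.62 and 11.5 mg/dL (2.65 to 2.87 mmol/L) and check whether any progression call or progression date depended on the unit used. The cost is one corrected figure and a short data query. No endpoint, sample size or analysis method changes.
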